Specific Aim #2: To demonstrate that 10 sessions of 40 Hz tACS stimulation decreases amyloid levels on PET imaging in patients with mild AD.

We hypothesize that 40 Hz tACS will result in a significant decrease in amyloid burden in the stimulated area.

Specific Aim #3: To demonstrate that 10 sessions of 40 Hz tACS stimulation improve resting-state EEG background activity, EEG connectivity, and performance on cognitive testing.

We hypothesize that 40 Hz tACS will result in a normalization of brain activity with increased high frequency (gamma) EEG activity and increased brain network connectivity, and that these changes will be associated with an improvement in memory and general cognitive function.

Exploratory Aim 1: As an exploratory aim, we will analyze the impact of APOE (Apolipoprotein E) and BDNF (Brain Derived Neurotrophic Factor) polymorphisms on individual response to tACS (i.e. change in amyloid level and/or gamma EEG spectral power), as measured via EEG and cognitive testing. Such information will be derived via saliva samples.

Exploratory Aim 2: The response to non-invasive brain stimulation might be related to intrinsic brain properties such as brain plasticity and connectivity levels (Freitas, Farzan, & Pascual-Leone, 2013). We will collect information on plasticity levels via a combined TMS and EEG recording session; responsiveness to tACS will be assessed via a combined tACS-EEG session.

B2. SIGNIFICANCE AND BACKGROUND FOR THE STUDY

Histopathologically, AD is characterized by diffuse amyloid- β (A β) plaques and phosphorylated tau (p-tau) deposition in neurofibrillary tangles, as well as widespread neurodegeneration. Recent PET imaging studies suggest that progressive amyloid deposition can begin up to 20 years before the onset of clinical symptoms and stabilizes around the time that clinical symptoms begin to be prominent (C. R. Jack et al., 2013; C.R. Jack Jr. et al., 2010); that tau is isolated to the lateral temporal lobes without amyloid, and spreads outside the lateral temporal lobes in patients with amyloid; and that neurodegeneration and clinical symptoms are correlated with the spread of tau (Pontecorvo et al., 2017). Consequently, the evidence suggests that both amyloid and tau play a critical role in AD pathogenesis, and interventions that reliably and safely decrease the intracerebral burden of amyloid or tau could potentially be of marked clinical importance.

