Normal cerebral activity is composed of oscillatory activity across a wide range of frequencies, with oscillatory activity in the 30-80 Hz range known as “gamma” activity. A consistent finding in patients with AD is a relative attenuation of such faster frequencies (Babiloni et al., 2015), and dysregulation of gamma activity linked to pathologic network hyperexcitability which is also seen in animal models of AD (Verret et al., 2012). More recently, a seminal study found that exogenously-induced 40 Hz gamma oscillations reduce A β levels and amyloid plaques, and may also reduce tau levels, as seen in a mouse model of AD (Iaccarino et al., Nature 2016). The same authors have also determined that in presymptomatic AD mice, induction of gamma activity remarkably prevents subsequent neurodegeneration and behavioral deficits, suggesting that gamma induction may represent a novel and powerful therapeutic approach for AD. This opens to the possibility of modulating gamma activity in humans, potentially leading to the same beneficial effects observed in mouse models. Work from our center has recently shown the possibility of modulating brain oscillatory patterns in AD patients, with changes in brain connectivity in the gamma band (measured with EEG) observed after administration of antiepileptic drugs (Musaeus, Shafi, Santarnecchi, Herman, & Press, 2017).

That being said, drug-based interventions do not allow for precise targeting of A β deposition, while the induction of 40Hz oscillations by means of visual and/or auditory stimulations (as those implemented in the aforementioned animal model by Iaccarino et al. 2016) are limited by the nature of the stimulation, i.e. they only affect visual and auditory cortices. PET imaging allows for characterization of individual patterns of A β deposition (see Figure 2), which might be present in various cortical sites not necessarily matching the regions of action of sensorial stimulation approaches. The present proposal will leverage current knowledge on transcranial electrical stimulation to collect preliminary data on an individualized intervention to reduce A β with greater spatial accuracy, by means of transcranial alternating current stimulation (tACS).

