and stored for future analysis of putative biomarkers. Local analysis of CSF will be done at LabCorp and will include cell count, glucose, and protein.

Blood Draw

The blood draw will be completed at baseline and follow-up for testing of the same biomarkers as tested in the CSF, such as, Aβ₄₂, Aβ₄₀, total tau, phospho-tau181, cytokines, YKL-40, and BDNF. These results will be used to correlate with the CSF results. In addition, if a patient opts not to undergo the lumbar puncture, the blood tests for biomarkers will provide valuable information. Blood draws will be collected in the Cognitive Neurology Unit or in the Clinical Research Center. A maximum of 20mL (approximately 10mL for the biomarkers and 10mL for CBC, glucose, and protein) will be collected and processed by the Clinical Research Center laboratory. If the participant has an LP, blood will be sent to LabCorp for a CBC with differential, glucose, and protein to correlate with the LP analysis for any abnormalities/possible incidental findings. The remainder will be frozen, and later batch-shipped to an outside laboratory for processing. Assays will be performed by the central biomarker laboratory. Blood samples will also be frozen and stored for future analysis of putative biomarkers.

tACS (Starstim Device)

tACS will be administered using a 32-channel device. The tACS will be applied daily for 60 minutes for 10 consecutive weekdays. The Starstim is also capable of recording EEG. Five minutes of eyes-closed and eyes-open resting state EEG will also be recorded before and after each stimulation session, to assess the degree of entrainment of gamma oscillations during each tACS stimulation session.

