tACS involves the administration of low-amplitude (< 2mA) sinusoidal electrical currents via scalp electrodes. Current will be applied in the gamma frequency (40 Hz) range to the regions of tracer uptake on the amyloid PET scan on a case-by-case basis. Although tACS is usually administered via bipolar montages using two large electrodes, such montages have poor spatial specificity. Our group has been at the forefront of efforts using multifocal (multielectrode) montages that can deliver higher amplitude and more spatially specific stimulation patterns (Ruffini, Fox, Ripolles, Miranda, & Pascual-Leone, 2014). Consequently, stimulation will be applied to the target region with maximum amyloid levels using individualized multifocal (multielectrode) montages to maximize the induced electrical current in the target region.

Stimulation will be slowly ramped up/down at the beginning/end of each stimulation session to minimize skin sensation. tACS can elicit phosphenes - a sensation of light caused by excitation of the retina by mechanical or electrical means rather than by light. Participants will be queried each day at the end of the visit to see if they experienced phosphenes. They will be informed that this may happen and will be informed that they are free to ask to stop participation if the phosphenes bother them. We anticipate that a low percent of participants will experience this sensation (10%).

B. Statistical Considerations

Sample Size Justification: Given the intrinsic difficulties in the care of AD patients and the commitment required by the multi-day tACS intervention, we expect an attrition rate higher than 20%, potentially close to 30%. We will compare individual changes in amyloid according to the aforementioned SUVR threshold. In order to get valuable pilot data about changes in PET markers, we aim to recruit up to 20 participants to account for attrition with 10 expected to enroll in the study. This would allow for a final sample of 5/6 fully characterized participants who will complete the tACS

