TMS-EEG and tACS-EEG analysis. Specifically, the TEPs will be studied using traditionally employed metrics such as the absolute magnitude and time-to-peak of the EEG signal, global mean field amplitude, power in various frequency bands, cortico-cortical coherence in various frequency bands, significant current density, phase-locking, and significant current scattering. Measures including spectral power, coherence and connectivity will be used to assess the impact of tACS on EEG dynamics. ANOVA will be used to determine whether these metrics vary as a function of brain region across subjects. The EEG functional connectivity will be assessed using a variety of different metrics, including cross-correlation coefficient, coherence, synchronization likelihood, transfer entropy, partial directed coherence, and Granger causality. These metrics will be calculated on EEG recorded during the eyes-closed resting state. Values will be obtained for multiple segments of data of various window sizes (generally on the order of 4 to 10 seconds to permit analysis of low-frequency bands) before and after rTMS and tACS; consequently, multiple data segments will be available in each period. Each statistical analysis will be based on a significance threshold equal to $p.0.05$, correction for multiple comparisons will be applied when needed by using Bonferroni correction, False Discovery Rate (FDR) or network-based statistics (NBS).

C. Subject Selection

Subjects will be recruited from BIDMC and outside providers and will have had an amyloid positive PET scan, or suspected amyloid burden.

Inclusion Criteria:

- Clinical Diagnosis of mild AD*
 - Clinical Dementia Rating (CDR) = 0.5 - 1
 - Mini Mental State Examination (MMSE) \geq 20
 - Demonstration or history of memory impairments.

* Confirmation of diagnosis will be made by the study MD based on a holistic consideration of the participant's cognitive evaluation and history.

- Previous amyloid positive PET imaging or suspected to be amyloid positive
- At least 45 years old
- Minimum of completed 8th grade education
- On a stable dose of medications for memory loss including cholinesterase inhibitors (e.g. donepezil, rivastigmine or memantine) as defined as 6 consecutive weeks of treatment at an unchanging dose
- No history of intellectual disability

Exclusion Criteria:

- Current history of poorly controlled migraines including chronic medication for migraine prevention

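### None of the EEG connectivity metrics named for Aim 3 is insensitive to zero-lag signal mixing, so a purely local gamma power rise can by itself be scored as increased connectivity

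*Combined protocol and SAP*

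**What the plan says.** Specific Aim #3 (section B1) hypothesises "increased high frequency (gamma) EEG activity and increased brain network connectivity" and ties both to better memory and cognition.

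The TMS-EEG and tACS-EEG analysis paragraph of section B3.B (Statistical Considerations) says "The EEG functional connectivity will be assessed using a variety of different metrics". Six are then given as examples, with none marked as primary: "including cross-correlation coefficient, coherence, synchronization likelihood, transfer entropy, partial directed coherence, and Granger causality". It adds: "These metrics will be calculated on EEG recorded during the eyes-closed resting state". Values are taken before and after stimulation on segments "generally on the order of 4 to 10 seconds to permit analysis of low-frequency bands". The Data Analysis paragraph tests pre-post changes in EEG metrics by paired t-test at 0.05. The sample size paragraph expects 5 or 6 completers with full data. There is no control arm for the 10-session intervention.

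Stimulation is focal by design: "stimulation will be applied to the target region with maximum amyloid levels using individualized multifocal (multielectrode) montages".

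For resting connectivity the documents do not mention volume conduction, a phase-lag or imaginary-coherence measure, a Laplacian, source-space estimation, leakage correction or adjustment for power. The EEG cleaning described for the TMS-EEG visit covers eye, jaw and forehead artifacts. Phase-locking and current density are listed, but for the TMS-evoked potentials. Bonferroni, FDR and NBS address multiplicity only.

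**The concern.** One cortical source reaches several scalp electrodes at the same instant. Cross-correlation, coherence and synchronization likelihood count that instantaneous similarity as coupling, so they depend on the power of the shared source relative to background. A pre-post comparison usually cancels this, because head geometry does not change between visits. It does not cancel here, because source power is the quantity that stimulation is meant to change.

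The lag-based metrics (transfer entropy, partial directed coherence, Granger causality) do not escape. If two electrodes are noisy copies of one autocorrelated signal, the past of one adds information about the present of the other beyond the latter's own noisy past. That reads as directed influence although there is none.

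At stake is whether the two halves of the Aim 3 hypothesis are separate findings. With these metrics alone, a connectivity result may only restate the power result.

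**Working it through.** The plan gives no connectivity effect size, power or variance, so there is no figure to reproduce.

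**Inputs from the documents.** Six metrics; 5 or 6 patients; paired t-test at 0.05 (sidedness not stated, two-sided assumed); segments of 4 to 10 s. The TMS-EEG section gives five minutes of eyes-closed recording: 300 s / 4 s = 75 segments. The tACS visits section gives three minutes: if that is per condition, 180 / 4 = 45. Channels: "tACS will be administered using a 32-channel device" (assumed to be the EEG montage as well).

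**Assumed, not in the documents.** Signal-to-noise ratio (SNR), size and spread of the power rise, source gains, background noise.

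**Step 1, closed form.** Two electrodes see one source plus independent noise, with no interaction. With R = source power / noise power, magnitude-squared coherence is C = (R/(1+R))^2. For a 50% power rise:

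- R from 1 to 1.5: C from 0.25 to 0.36 (0.36/0.25 = 1.44, +44%).
- R from 0.5 to 0.75: C from 0.11 to 0.18 (0.1837/0.1111 = 1.65, +65%).

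**Step 2, rejection rates.** Same model, 75 four-second segments, median power rise 50%, between-patient SD 0.3 on the log scale, 1,000 simulated trials per setting, t = mean(d)/(SD(d)/sqrt(n)). The ranges span repeated runs:

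| Metric | n = 5 | n = 6 |
|---|---|---|
| Coherence, several bins averaged | 42-58% | 55-74% |
| Coherence, single bin | 25-36% | 34-47% |

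Debiased weighted phase-lag index (wPLI) rejected in 2-7% across settings. With no power change, coherence rejected in about 5%. These rates are for one uncorrected comparison.

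**Step 3, all six metrics, n = 6.** One 40 Hz source, unequal gains (0.6-1 and 0.3-1), autoregressive background, 8 s segments, no interaction. Probability of a significant rise (two values = two directions):

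| Metric | no power change | power x1.5 | power x2 |
|---|---|---|---|
| Cross-correlation | 0.03 | 0.98 | 1.00 |
| Coherence | 0.02 | 0.95 | 1.00 |
| Synchronization likelihood | 0.01 | 0.60 | 0.96 |
| Transfer entropy | 0.05, 0.05 | 0.60, 0.40 | 0.80, 0.58 |
| Partial directed coherence | 0.02, 0.05 | 0.82, 0.56 | 0.92, 0.90 |
| Granger causality | 0.03, 0.04 | 0.88, 0.44 | 0.96, 0.89 |

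The power rise varies less between patients here than in step 2 (log SD of the change 0.15 x sqrt(2) = 0.21, against 0.3), which is one reason the rates are higher. The step 2 rates are the more cautious ones.

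**Step 4, 32 channels.** With 200 independent sources, a smooth lead field and power doubled in one local patch, mean coherence among the six nearest channels rose at every target site in all nine settings, by 0.017 to 0.053 on average. Averaged over all pairs, the rise was only 0.0005 to 0.0080 and occurred at 63-100% of sites; 33-91% of individual pairs rose.

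**Step 5, exceptions.** Where a pair was already dominated by another shared source and the rising source reached only one channel, all six metrics fell (coherence 0.82 to 0.33). At very high SNR, transfer entropy and Granger causality fell (Granger 0.095 to 0.07).

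**Step 6, candidate replacements.**

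- Signed imaginary coherence: for a true coupling rise (0.3 to 0.9, 60-degree lag) with the lead/lag sign random by patient, n = 6, it detected the rise in 3-6% of trials; debiased wPLI detected it in 99.8%.
- Absolute imaginary coherence: its noise floor moves with power. In the step 3 model it gave a significant fall in 13% (x1.5) and 39% (x2) of trials.
- Debiased wPLI with constant lagged coupling of 0.7, SNR 1 and a median 50% power rise: it went from about 0.30 to about 0.42 and rejected in 18-59% of trials, depending on how many bins were averaged.

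**The case against.** The strongest reply has four parts.

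- **The list is open.** It is introduced as a variety of metrics with six as examples, and the documents do not say whether connectivity is computed at electrodes or in source space. A reader might infer that the plan rules out a protected metric or commits to electrode-level analysis. It does neither. What stands is that none is named, none is primary and no leakage step is stated.
- **The direction is not guaranteed.** A reader might infer that any gamma rise will be scored as connectivity, or that any observed connectivity rise must be an artifact. Steps 2, 4 and 5 contradict the first, and nothing in the documents supports the second. All magnitudes rest on assumed SNR and power rises.
- **Power is already analysed.** Spectral power, coherence and connectivity are all listed, with an ANOVA by brain region. This is fair, but no rule says how a connectivity change is to be read when power has also changed.
- **This is a safety and feasibility pilot.** Connectivity is one component of the third aim, and no safety, feasibility or PET conclusion depends on it. That limits the weight of the point. It does not remove it: the protocol states a directional connectivity hypothesis, tests it at 0.05, and expects later studies to follow from this one.

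It is also fair to say that no replacement is fully clean. Step 6 shows that debiased wPLI keeps some dependence on SNR when lagged coupling is truly present.

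**Conclusion.** The point holds as a possibility. As written, the planned metrics cannot separate the two effects that Aim 3 predicts, and a local power rise alone can be reported as increased connectivity. With SNR 0.5 to 1, a median 50% power rise, 75 four-second segments and several bins averaged, the false significant rise for coherence is roughly 40-55% with 5 patients and 60-70% with 6. For debiased wPLI it is about 5%. Single-bin coherence, fewer segments or multiplicity correction would lower the coherence rates; a larger or more uniform power rise would raise them. Because this is bias and not noise, more patients would make it worse.

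The effect is concentrated near the target and small when averaged over the whole scalp. The change is worth making because it is cheap, but the point does not threaten the trial's main conclusions.

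**What to change.** In the TMS-EEG and tACS-EEG analysis paragraph of section B3.B:

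1. Name one primary metric for the Aim 3 connectivity claim: the debiased weighted phase-lag index in the gamma band on eyes-closed resting EEG, with the electrode pairs fixed in advance. Signed imaginary coherence should not be used: its sign shows which electrode leads, and this can cancel across patients whose targets are individualized. Its absolute value should not be used either, because its noise floor shifts with power.
2. Report the six listed metrics as descriptive.
3. Report the change in gamma power at the same electrodes alongside, and claim increased connectivity only if it persists after accounting for that change. A between-patient regression with 5 or 6 patients leaves 5 - 2 = 3 or 6 - 2 = 4 residual degrees of freedom. A within-patient approach, such as comparing pre and post segments of similar band power, may therefore be more practical, although such matching is only approximate.

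Cost: protocol wording and a standard routine on data already being collected, with no added visits or burden. Downside: true zero-lag coupling is missed, and some residual dependence on power remains and should be stated in the report.

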Moreover, new technologies developed by our center in collaboration with external partners (Neuroelectrics, Barcelona, Spain) might help to further increase the precision of tACS targeting, allowing for individualized stimulation solutions based on modeling of current distribution using structural MRI scans. The first generation of devices for transcranial electrical stimulation only allowed for stimulation protocols including two electrodes, limiting the number of target regions to no more than two. Moreover, this solution did not allow for careful mapping of individual brain anatomy, and therefore resulted in sub-optimal stimulation patterns. Current approaches for so-called multi-focal stimulation (Ruffini, Fox, Ripolles, Miranda, & Pascual-Leone, 2014) permit stimulation montages based on up to 32 stimulating channels, with the precise stimulation pattern defined by means of modeling of induced electric field based on individual T1-weighted MRI scans. This results in more accurate, individualized montages, which might become crucial when targeting amyloid in AD patients.

Also, genetic testing is increasingly playing a role in the understanding of the etiology of AD. In particular, certain polymorphisms in the gene which codes for the apolipoprotein E (ApoE) have been linked to increased risk of developing AD, specifically with carriers of the $\epsilon 4$ allele (Risacher et al., 2013). Furthermore, there is at least some evidence that ApoE- $\epsilon 4$ may impact response to non-invasive brain

stimulation (Peña-Gomez et al., 2012), therefore potentially modulating the effect of tACS.

This study will leverage all this accumulated knowledge by implementing an intervention based on multiple, individualized multifocal tACS stimulation sessions based on individual PET and MRI information in patients with amyloid-positive PET.

B3. DESCRIPTION OF RESEARCH PROTOCOL

A. Study Design – Overview, Methods, Procedures

Overview

This is a safety and feasibility study of tACS in patients diagnosed with early AD. Individuals who have had amyloid PET imaging and have evidence of cerebral amyloid burden will be recruited. Individuals with a diagnosis of mild Alzheimer's Disease and suspected amyloid burden will also be recruited and undergo a PET scan during the screening process. All subjects will receive 10 sessions of active tACS targeted on a case-by-case basis to the regions of tracer uptake on the amyloid PET study.

Study Design

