- National Alzheimer's Coordinating Center's Uniform Data Set (NACC-UDS) battery that includes the MoCA, Number Span Forward & Backward, Trail Making Test, Figure Copy, Story Recall, Digit Symbol, and Multilingual Naming Test, Verbal Fluency, Category Fluency. Only portions of this set may be completed, although the number span will be done in all cases. The MoCA will serve as the baseline cognitive assessment for monitoring cognition throughout the study.
- Brief estimate of intelligence using the Wechsler Test of Adult Reading (WTAR)
- Rey Auditory Verbal Learning test (RAVLT) as measure of learning and memory
- Modified Edinburgh Questionnaire to determine handedness
- Pregnancy test for females of child-bearing potential
- Saliva for DNA and tau (this may be collected at any visit)
 - Three saliva samples will be taken:
 - One sample for tau protein
 - Two optional samples for BDNF and APOE genotyping (this may be collected at visit #2 if the subject has trouble producing additional saliva following the first collection)
- fMRI - Patients who have had an fMRI in another study in the Berenson-Allen Center within 6 months (pending the quality of the images) may not have to repeat this scan
- PET Imaging
- Lumbar puncture** (optional)
- Blood draw**
- TMS-EEG plasticity assessment
- tACS-EEG recording with cognitive tasks

The screening and baseline visits will occur over 4-5 days. All of the screening activities necessary for determining inclusion and safety will be completed on the first day as indicated by the asterisks above (*). The remainder of the activities will be planned according to scheduling, resources, timing and subject tolerability. It is possible that there would be an additional visit due to these issues. It is possible that a baseline activity will happen on the first day of stimulation prior to the tACS (e.g. a questionnaire).

**If the participant agrees to an LP, blood and CSF will be sent for real-time analysis (e.g. Labcorp) of CBC, glucose, and protein to assess for any incidental LP finding such as indicators that there is concern for an inflammatory process. CSF and blood will also be processed and stored for analysis of AD biomarkers at the end of the study. If the participant does not agree to the LP, the blood will only be analyzed for AD biomarkers at the end of the study.

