Participants will be informed of their baseline amyloid imaging results as the scan must be positive to be included in the study. The study investigator will inform the participant if the scan was positive or negative and will be clear with the participant that this scan was collected for a research study. If participants would like to understand how their results relate to their diagnosis or care, they can opt to have the results shared with their provider. The scans are all collected and read in the same manner that they would be if done clinically. If participants are in agreement that they would like to share the scan results with their provider, the study team will work with them to provide this information to their care provider. If they do not have a provider who is comfortable with relating the results to the subject's care or if they do not have a provider, the study team will work with them to arrange an appointment in the Cognitive Neurology Unit.

If patients have had a clinical or research amyloid PET at BIDMC, we may use these results as a measure of amyloid progression.. If patients have had a clinical PET at an outside hospital, we may ask them to obtain a copy to compare with the current study.

TMS – EEG: Brain plasticity and responsiveness to stimulation

The TMS-EEG measures will be collected at baseline and then again following the 10 day tACS intervention to assess for changes in neural plasticity. Subjects will be set up in a chair with an EEG cap and with EMG electrodes placed on the right hand for collection of motor evoked potentials (MEPs) during stimulation over the left primary motor cortex (M1). The EEG cap and EMG electrodes will remain in place throughout the TMS session. EEG will be recorded throughout the session.

Participants will be provided ear protection to be worn throughout the session. TMS specific adverse effect review will be reviewed prior to and at the end of the session.

- **Baseline Resting State EEG and artifact recording:**

Baseline resting state EEG and artifact recordings will be obtained with the eyes open for five minutes and then eyes closed for five minutes. Subjects will be asked to briefly move their eyes, clench their jaws, and tense their foreheads so that the EEG artifacts associated with these movements can be recorded and similar artifacts removed from the remaining EEG recordings.

- **Assessment of Motor Threshold:**

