Medical History Review	X*														X		
Medication Review	X*														X		
TMS & tACS safety questionnaires	X*																
MMSE	X*														X		
CDR	X*																
Inclusion/ Exclusion Review	X*																
MRI Screening Questionnaire		X															
ADAS-Cog		X													X		
CGIC		X													X		X
NACC-UDS		X													X		X – ADL only
WTAR		X*													X		
RAVLT		X													X		
Edinburgh Handedness		X															
Pregnancy Test (if applicable)		X															
Saliva (optional)		X															
fMRI		X													X		
PET		X													X		
Resting State EEG		X															
Lumbar Puncture (optional)		X													X		
Blood Draw		X													X		
TMS-EEG		X													X		
tACS-EEG		X													X		
Review of side effects/ adverse events				X	X	X	X	X	X	X	X	X	X	X	X		
Cap set up				X	X	X	X	X	X	X	X	X	X	X			
tACS (1 hour)				X	X	X	X	X	X	X	X	X	X	X			
Cognitive Assessment				X	X	X	X	X	X	X	X	X	X				X
Participant Experience Assessment															X		

* = these procedures must be completed on screening day 1

A = screening procedures may be completed over 4-5 days according to resources, timing and subject tolerability with the exception of the procedures necessary for determining inclusion and safety as indicated by *

B = follow-up procedures may be completed over 4-5 days according to resources, timing and subject tolerability. A 1 month and 3 month phone follow up of cognition and function will be completed

B4. POSSIBLE BENEFITS

It is not possible to predict whether subjects will benefit directly from participation in this study. Participation in the study may help others in the future as a result of knowledge gained from the research.

B5. POSSIBLE RISKS AND ANALYSIS OF RISK/BENEFIT RATIO

TMS

TMS has been used in a growing number of laboratories worldwide for over twenty years, and safety guidelines have been developed to prevent potential side effects. In the present study, all recommended safety precautions for TMS will be strictly adhered to by the investigators. The subject will be monitored for adverse reactions during and following the treatment.

Even though all known safety precautions will be implemented as part of the present protocol, the following side effects and discomforts might occur:

More Common:

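### Amyloid PET decides inclusion but is not scheduled as an eligibility step, so a patient without a prior positive scan can have lumbar puncture, TMS-EEG with iTBS and tACS-EEG before being found ineligible

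*Combined protocol and SAP*

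**What the plan says.** The protocol describes amyloid status at entry in four places.

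- **B3.C, Inclusion Criteria:** "Previous amyloid positive PET imaging or suspected to be amyloid positive". The sentence that introduces subject selection offers the same two routes.
- **B3.A, Methods, PET:** "Participants will be informed of their baseline amyloid imaging results as the scan must be positive to be included in the study".
- **B3.A, Overview:** patients with a mild AD diagnosis and "suspected amyloid burden will also be recruited and undergo a PET scan during the screening process".
- **B3.A, Screening and Baseline Visit (Visits 1-4):** "All of the screening activities necessary for determining inclusion and safety will be completed on the first day as indicated by the asterisks above". For everything without an asterisk, "The remainder of the activities will be planned according to scheduling, resources, timing and subject tolerability".

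Footnote A of the Study Visit Schedule repeats the day-1 rule. Screening may be spread over 4-5 days, "with the exception of the procedures necessary for determining inclusion and safety as indicated by" an asterisk. In both the screening list and the schedule, the inclusion/exclusion review has an asterisk, while PET, lumbar puncture, TMS-EEG and tACS-EEG have none.

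**The concern.** The inclusion list and the PET subsection set different conditions for the same decision. On the list, suspicion of amyloid is enough. In the PET subsection, only a positive scan is. The scheduling rule widens the gap, because it says that all procedures deciding inclusion are finished on day 1 and then leaves out the one test on which inclusion depends for a patient not previously scanned.

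What is at stake is avoidable exposure. Patients in this trial are described as potentially vulnerable (B6, Subject Protection), and B4 says direct benefit cannot be predicted. Someone who turns out to be amyloid-negative may already have had an optional lumbar puncture, theta-burst stimulation and test blocks of tACS, in a study that he or she could not join. Accounting is a second, smaller matter: a patient lost because of a negative PET is a screen failure, and the plan does not separate that from attrition during tACS.

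**Working it through.** The plan has no figure to reproduce here. The check is textual, with one division at the end.

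1. **Who is concerned.** Only patients who enter as suspected cases. A patient with a previous positive PET meets both statements.
2. **Does the inclusion list admit them?** Yes. The criterion joins the two routes with an *or*. No exclusion criterion names a negative scan. The nearest is the general one on suitability in the investigator's opinion, which is discretionary.
3. **Does another section say otherwise?** Yes. The PET subsection makes a positive scan a condition of inclusion. It also foresees negative results, since the participant is told either way, but no text says what then happens to that participant.
4. **When is inclusion settled?** By the asterisk rule, on day 1. The only scheduled inclusion/exclusion review falls on that day, and nothing requires the PET result to be available by then.
5. **What may come before the PET?** Lumbar puncture, TMS-EEG and tACS-EEG are all unasterisked, so their order is left to logistics. Their own Methods subsections do not make them conditional on the scan. The TMS-EEG session includes iTBS of 600 pulses to the motor cortex. Lumbar puncture could not replace the PET for eligibility, because the CSF markers of AD are analysed at the end of the study.
6. **What guards the ten tACS sessions?** The Overview puts the PET within screening. Study Design aims at people with raised amyloid on PET. The PET subsection speaks of a scan obtained before enrollment and requires it to be positive. The tACS subsection takes the stimulation target from the scan. Together these cover the main intervention, but none of them puts the PET result ahead of the three baseline procedures.
7. **Size per person, from B5.** With TMS, headache or neck pain in up to 20-40%. With lumbar puncture, headache in about 5%, typically mild, and persistent low-pressure headache in 1-4%.
8. **Number of persons.** This would be (entrants without a prior positive PET) x (proportion of them PET-negative) x (proportion of those who have at least one of the three procedures before the PET). The documents give none of the three terms. The ceiling of 20 participants only bounds the first, so no count follows.
9. **Radiation cost of an earlier scan, from B5, PET.** 24 mSv / 3 scans = 8 mSv per scan.

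**The case against.** The best defence is that the intent is plain. Read together, the Overview, Study Design, the PET subsection and the tACS targeting text make suspicion of amyloid a route to the screening PET and not a substitute for it. That stands, and it is why the point is confined to the baseline procedures. A reader might infer from the inclusion list that amyloid-negative patients could receive the 10-session course and dilute the Aim 2 population. Those sections do not support that reading.

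It can also be said that the asterisks are loose. In the schedule the WTAR has one, while the pregnancy test, which does decide eligibility, has none. So the missing asterisk on PET need not be deliberate. That is fair, but it shows that the day-1 rule needs correcting, not that the PET comes first. The printed lists do place PET above lumbar puncture, TMS-EEG and tACS-EEG, yet the text says the order is flexible. Conversely, a reader might take the shared schedule column as evidence that these procedures happen together. It is not: nearly all later baseline items fall in that column, although they are spread over 4-5 days.

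Finally, lumbar puncture is optional, and scanning first is a trade-off: some patients would be irradiated and then decline or fail to tolerate the other baseline procedures. Both points stand.

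**Conclusion.** The concern holds in a limited form. The inclusion list, the PET subsection, the screening section and the schedule disagree on what settles inclusion, and nothing makes the optional lumbar puncture, TMS-EEG with iTBS or tACS-EEG wait for the PET result. A patient without a prior positive PET can therefore undergo them and then prove ineligible. This should be corrected, because it arises from following the text as written and the remedy adds no procedure.

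The per-person risks are those stated in B5; the conclusion does not rest on an assumed rate. Two further inferences should be resisted. A reader might multiply the 20 places by a guessed negative-scan rate; that would also assume that every entrant is a suspected case and that every negative patient has the other procedures first, and the documents support neither. A reader might also cite the seizure risk of less than 1 in 1000 that B5 gives for repetitive TMS. The same item describes the risk with the theta-burst protocol used here as apparently negligible, so that figure should carry no weight.

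**What to change.** Reconcile the inclusion list, the PET subsection, the screening section and the visit schedule, as follows.

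- Word the criterion as an amyloid-positive PET, either previous or obtained at screening, with suspected amyloid serving only as a route to the screening PET.
- List a negative PET as a screen failure.
- For patients without a prior positive PET, complete the inclusion/exclusion check on the PET result before lumbar puncture, TMS-EEG and tACS-EEG, and amend the asterisk rule and footnote A to match.
- State which reading decides positivity for inclusion. The PET subsection describes a physician's read, while Statistical Considerations defines positivity as a global SUVR of at least 1.6.
- Report PET screen failures separately from tACS attrition. Statistical Considerations explains its expected attrition of more than 20%, potentially close to 30%, by the difficulty of care and the commitment required, and makes no mention of negative scans.

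The cost is wording, less freedom in scheduling the 4-5 baseline days, a wait for the PET read, and about 8 mSv for some patients who later decline or cannot tolerate the remaining baseline procedures.
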